13.4.4 Procedures

Chest X-ray will be performed at a collaborating radiology imaging facility as part of the screening. If a chest X-ray result is abnormal and considered by the investigator to be clinically significant, it will be up to the investigator's discretion if the subject should be enrolled into the trial.

The procedure may be omitted if a chest x-ray has been performed within 6 months before screening and the result is accessible and normal.

Punch biopsies will be performed as optional procedures. A supplementary informed consent form must be signed. A lesional and a non-lesional 4 mm punch biopsy will be performed in local anesthesia (approximately 1 mL/per injection 2% lidocaine with epinephrine solution) according to institutional guidelines. The punch biopsies will be performed at baseline and at visit 3 / 6 Weeks. Subjects will have the option to accept or decline punch biopsies. The acceptance or rejection of this procedure does not otherwise affect the eligibility of subjects. Punch biopsies will be snap frozen in liquid nitrogen and stored at -150°C for later analysis of IL-17 downstream pro-inflammatory marker genes (e.g. Nfkbia, CCL20, Defb4) by qPCR.

13.4.5 Research biobank

Samples of plasma (4 mL) are collected for storage in a research biobank at visit 1 (screening) and visit 3 (week 6). Optional skin punch biopsies are collected at baseline and visit 3 (week 6).

Purpose of the research biobank is to store the biological material safely until analysis of inflammatory markers can be performed in all samples.

Termination of the research biobank: January 2020.

Any remaining biological materials after this date will be anonymized or destroyed.

13.5 FDG-PET/CT assessments

13.5.1 Patient preparation

FDG-PET/CT will be performed after an overnight fast using a combined PET/CT scanner (Siemens Biograph 64 PET/CT (Siemens, Germany)). FDG will be administered intravenously (approximately 200 MBq) and patients will rest comfortably for approximately 90 to 120 min in a well-tempered environment.

Trial ID (EudraCT No.): 2017-003697-14	Date: 23.02.2018	Page Version 2.3
---	------------------	---------------------

13.5.2 FDG dose and circulation time

For arterial imaging with PET, longer delays between FDG injection and PET imaging than those used for oncology are recommended to allow sufficient FDG accumulation in the arterial wall and to reduce the intensity of FDG signal in the blood. The FDG circulation time is critical as optimal contrast between the target (plaque, arterial wall) and the background (blood) is essential to ensure accurate quantification of plaque FDG uptake. Based on previous results and current recommendations,⁴⁵ **the acquisition of PET images is performed 2 hours after injection.** This imaging delay represents the best compromise between a low background signal in blood and an acceptable duration of the PET study for patients.

To obtain a radiation dose as low as reasonably achievable, a **200 MBq protocol** has been adopted. It has previously been shown that low-radiation-dose protocols can be used in arterial FDG-PET imaging without undue degradation of either image quality or lesion quantification.⁶²

13.5.3 Pre-scan fasting glucose

Fasting glucose will be assessed before FDG-PET/CT. Vascular imaging should ideally be performed in patients with prescan glucose levels lower than approximately 7.0 – 7.2 mmol/l. In patients in whom these blood glucose levels cannot be achieved, correction of the vascular FDG uptake according to the EANM recommendations for oncological PET imaging will be considered at the discretion of the nuclear medicine expert investigator.

13.5.4 Image acquisition

A low dose CT from the skull base level to the lower spleen level will be performed first for attenuation correction and anatomical co-registration. Imaging of the entire aorta, spleen and truncal adipose tissue will be performed next over 15–30 min (1 or 2 bed positions) acquisition time depending on the patient's anatomy.

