Furthermore, we have recently conducted a study demonstrating increased splenic inflammation in patients with psoriasis compared with age-matched control subjects. Additionally, a significant association between splenic inflammation and aortic wall inflammation was found in psoriasis patients (unpublished data). Other exploratory studies indicate a role of the spleen in atherosclerosis-associated immunity,^{37,38} and cardiovascular clinical studies indicate that a cardio-splenic axis exists.³⁹ Given the well-established role of the spleen in systemic inflammatory diseases, this provides evidence of systemic inflammation in psoriasis beyond that reported by biomarker studies.

Recently, in an open-label cohort of patients with mild-to-moderate psoriasis it was shown that reduction of skin inflammation by mixed interventions was associated with improvement in aortic wall inflammation assessed by FDG-PET/CT.⁴⁰ This finding was not corroborated by two RCT's assessing the effect of anti-TNF drug adalimumab on aortic wall inflammation as no significant difference was found after 16 weeks of treatment.^{41,42} However, a limitation of these studies were that the primary endpoint was changes in FDG-uptake in only the ascending part of aorta and not the entire vessel.⁴³ Choosing the ascending aorta as the representative aortic segment may not always be the optimal approach. For example, Besson et. al. investigated the performance of different semiquantitative measures to distinguish controls from patients with large vessel vasculitis and found that TBR performed well in all segments of the aorta – except in the ascending aorta.⁴⁴ In line with this, we also recently found increased aortic wall inflammation in psoriasis patients compared with controls without inflammatory diseases in all segments of the vessel except the ascending part.³⁴ It has previously been suggested that whole-vessel aortic mean TBR_{max} is well suited as a marker of cardiovascular risk for assessment of global arterial inflammation.⁴⁵

Taken together, these studies establish FDG-PET/CT as a feasible technique for visualizing vascular inflammation and systemic inflammation as well as changes in vascular/systemic inflammation in psoriasis.

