8.8 Exposure to radiation

During FDG-PET/CT, the patients are exposed to ionising radiation in the amount of 4.8 mSv at each imaging procedure. In case of repeat scan after 16 weeks, this means that the subjects are exposed to a total amount of 9.6 mSv.

To minimize the exposure to ionizing radiation a low radiation dose protocol of 200 Mbq FDG is used. To avoid loss of data quality the low radiation dose protocol is combined with an extended PET acquisition time. This particular PET protocol implies a radiation dose of 3.8 mSv. Additionally, non-contrast low radiation dose CT is performed from just above the level of the aortic arch to the lower spleen level for attenuation correction and anatomical co-registration. The radiation dose associated with this part of the procedure is 1.0 mSv.

The total radiation dose for a subject completing the trial is thus: (2 x 3.8 mSv (PET) + 2 x 1.0 mSv (CT)) = 9.6 mSv. Background radiation in Denmark is approximately 3 mSv per year. The exposure to radiation in this study corresponds to 3-4 years of average background radiation. The additional cancer risk associated with the radiation exposure in this study is 0.048%. An additional cancer risk of 0.048% is equal to approximately 1 in 2080 chances. In a healthy individual younger than 50 years of age, the exposure of 9.6 mSv will increase the lifetime risk of dying from cancer from 25% to 25.048%.

Trial ID (EudraCT No.): 2017-003697-14	Date: 23.02.2018	Page Version 2.3
---	------------------	---------------------

There is no risk of deterministic effects in this study. The risk of stochastic effects is estimated to category IIb.

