8.9 Benefit/risk assessment

There is an unmet medical need to reduce the increased risk of cardiovascular disease in patients with psoriasis. Cardiovascular disease caused by premature atherosclerosis is the cause of morbidity and decreased quality of life as well as increased mortality in patients with psoriasis. Due to the high prevalence of the disease this is relevant to a large number of patients. Brodalumab targets IL-17RA which has been shown as a key receptor in psoriasis patogenesis and a promising target in atherosclerosis.

Brodalumab has already demonstrated high efficacy and a favorable safety profile in the treatment of moderate-to-severe psoriasis in clinical studies. The drug is approved for the treatment of moderate-to-severe psoriasis by EMA and DMA.

In order to ensure appropriate treatment of the patients after they have completed the trial, the subjects will be treated at the investigator's discretion or referred to other physicians according to clinical practice and national treatment guidelines.

In patients undergoing FDG-PET/CT, it is well known that incidental focal lesions can be indicative of premalignant or malignant lesions. For instance, studies have shown that FDG-PET/CT reveals unexpected colonic FDG uptake in approximately 5% of patients and that a considerable number of these are diagnosed as premalignant or malignant.⁴⁷⁻⁴⁹

A high frequency of incidental PET findings have previously been shown in psoriasis patients.⁵⁰

We found incidental focal colorectal FDG-uptake in one of 12 cases in our pilot study of aortic vascular inflammation in patients with moderate-to-severe psoriasis.³⁴ This particular case of asymptomatic colorectal cancer was diagnosed earlier than would have been the case if the patient had not undergone FDG-PET/CT. The cancer was curably removed by surgery.

In the current study, the low-dose FDG-PET/CT protocol will limit the area of interest to the thoracic and upper abdominal area.

The main risk in this study is associated with the exposure to radiation. A low radiation dose PET protocol and a limited non-enhanced CT protocol has been adopted to reduce the radiation dose to a minimum without sacrificing data quality.⁵¹

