9.1 Trial objectives and endpoints

Objectives	Endpoints
Primary objective To assess the change in aortic wall inflammation from baseline to week 16 in brodalumab treated psoriasis subjects compared to placebo.	Primary endpoint 
 Change in the average of maximum TBR values (MeanTBR_{max}) of the entire aorta from baseline to week 16
Secondary objectives To assess the change in splenic inflammation from baseline to week 16 in brodalumab treated psoriasis subjects compared to placebo. To assess the change in aortic wall subsegment inflammation from baseline to week 16 in brodalumab treated psoriasis subjects compared to placebo. To assess whether changes in skin inflammation is associated with changes in aortic wall inflammation and/or changes in splenic inflammation.	Secondary endpoint 
 Change in the spleen-to-liver ratio (SLR) based on splenic and liver mean standardised uptake values (SUV_{mean}) Change in the average of maximum TBR values (MeanTBR_{max}) of the ascending, aortic arch, descending, suprarenal, and infrarenal aorta from baseline to week 16 Association between change in PASI and change in aortic wall MeanTBR_{max} Association between change in PASI and change in SLR
Additional secondary objectives To assess the change in subcutaneous adipose tissue inflammation from baseline to week 16 in	
 Change in the average of maximum SUV values (MeanSUV_{max}) of the abdominal

Trial ID (EudraCT No.): 2017-003697-14	Date: 23.02.2018	Page Version 2.3
---	------------------	---------------------

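### The CT used for attenuation correction stops at the lower spleen, but the primary and infrarenal endpoints are read down to the aortic bifurcation

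*Protocol*

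**What the plan says.** The CT part of the FDG-PET/CT is described in two places.

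- Section 13.5.4: "A low dose CT from the skull base level to the lower spleen level will be performed first for attenuation correction and anatomical co-registration".
- Section 8.8: "non-contrast low radiation dose CT is performed from just above the level of the aortic arch to the lower spleen level". It serves the same purpose there, and its dose follows: "The radiation dose associated with this part of the procedure is 1.0 mSv".

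Section 8.9, in a discussion of incidental findings, adds that "the low-dose FDG-PET/CT protocol will limit the area of interest to the thoracic and upper abdominal area".

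The endpoints need a longer range. In section 9.1 the primary endpoint is the change in MeanTBRmax "of the entire aorta from baseline to week 16", and the infrarenal aorta is one of five named subsegments among the secondary endpoints. Sections 15.4.1 and 15.4.2 repeat these regions. The sentence after the CT limits in 13.5.4 says "Imaging of the entire aorta, spleen and truncal adipose tissue will be performed next". Section 13.5.5 reconstructs attenuation-corrected images. Section 13.5.6 fuses PET with CT and measures the aorta every 3 mm from above the valve to the bifurcation, about 200 slices per patient.

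**The concern.** The CT is the stated basis for attenuation correction and for locating the vessel. Its lower limit is the lower spleen, while the aortic readings run to the bifurcation. The protocol describes no second or extended CT.

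Whole-vessel coverage is central to this trial's rationale. Section 8.3 criticises two earlier randomised trials because "the primary endpoint was changes in FDG-uptake in only the ascending part of aorta and not the entire vessel". If staff set the scanner by the written CT limits, the lower part of the aorta would have no CT behind it. A gap at the baseline scan could not be recovered once treatment had started.

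There is a second consequence. The CT dose in section 8.8 is stated for a range that reaches neither the bifurcation nor, at the top, the skull base named in 13.5.4. Section 8.9 calls radiation the main risk of the study, so it should be clear which scan the figure describes.

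**Working it through.** **1. The stated limits side by side**

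| Item | Section | Upper limit | Lower limit |
|---|---|---|---|
| CT | 8.8 | just above the aortic arch | lower spleen |
| CT | 13.5.4 | skull base | lower spleen |
| Area of interest | 8.9 | thorax | upper abdomen |
| Imaging after the CT | 13.5.4 | entire aorta | entire aorta |
| Aortic measurement | 13.5.6 | above the aortic valve | aortic bifurcation |
| Primary endpoint | 9.1 | entire aorta | entire aorta |
| Lowest secondary segment | 9.1 | infrarenal aorta | infrarenal aorta |

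The two CT descriptions agree on the lower limit, and that limit is shorter than the measurement range. They disagree on the upper limit. The upper limit affects no aortic endpoint, but it does affect which range the dose belongs to.

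**2. What an uncovered stretch is worth**

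Inputs from 13.5.6: about 200 slices, 3 mm apart. Assumption: every slice has equal weight in the average.

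- Measured length: 200 × 3 mm = 600 mm.
- Weight of one slice in the primary average: 1/200 = 0.5%.
- Slices per centimetre: 10 mm / 3 mm = 3.33.
- Weight of one centimetre: 3.33/200 = 1.7%.

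The protocol gives no distance from the lower spleen to the bifurcation, so the total share cannot be derived from it. As an illustration only, with assumed gaps:

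| Assumed gap | Slices without CT | Share of primary average |
|---|---|---|
| 60 mm | 20 | 10% |
| 90 mm | 30 | 15% |
| 120 mm | 40 | 20% |
| 150 mm | 50 | 25% |

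Of the five subsegments, one (infrarenal) would be mostly or wholly affected under the same anatomical assumption.

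**3. The dose statement**

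Inputs: PET 3.8 mSv and CT 1.0 mSv per scan, two scans (8.8); population risk 5% per Sv (8.10).

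- Total: 2 × 3.8 + 2 × 1.0 = 9.6 mSv, as the protocol states.
- Risk: 0.0096 Sv × 5%/Sv = 0.048%, which reproduces the protocol: "The additional cancer risk associated with the radiation exposure in this study is 0.048" per cent.

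The arithmetic is correct for a 1.0 mSv CT. What is unsettled is the scan range to which that 1.0 mSv applies.

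**4. Sample size, to mark the limit of the concern**

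Section 15.1 assumes means of 2.4 and 2.1, SD 0.35 and alpha 0.05, here two-sided as in 15.4.1. The normal approximation gives 22 per arm, with power 81.1% at n = 22. The t-test version gives 79.3% at n = 22. The plan's figure reproduces, and the CT range does not enter it.

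**The case against.** The best reply is that the intent is plain. Section 13.5.4 itself says the entire aorta is imaged, and sections 9.1, 13.5.5 and 13.5.6 all assume it. Staff would have to follow one sentence literally and ignore the next, so this is a wording slip whose harm is conditional and cannot be sized from the document. The reply adds that section 8.9 is about how much of the body is surveyed for incidental findings and is not an acquisition limit, and that nothing shows the 1.0 mSv to be wrong.

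Much of this stands. The intent is clear, and the CT limit is the likelier error. Section 8.9 is supporting context and does not carry the weight of the two CT descriptions. The harm does depend on anatomy that the protocol does not give, and no error in the dose has been shown.

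It does not remove the contradiction. The sentence on the entire aorta describes the acquisition that follows the CT, so it does not lengthen the CT. The shorter lower limit appears in two separate CT descriptions, which makes a single slip less likely. Clear intent shows which text is probably wrong, but it does not correct the instruction on which the scan and the dose statement rest.

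**Conclusion.** The inconsistency is real and should be corrected. As written, the only CT described for attenuation correction and anatomical matching does not reach the lower end of the aorta over which the primary endpoint and the infrarenal secondary endpoint are measured.

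The size is 0.5% of the primary average per uncovered slice, or about 1.7% per centimetre, with one of five subsegments mostly or wholly affected. The textual mismatch is certain. Its practical effect rests on two assumptions: that the bifurcation lies below the lower spleen, and that the stated CT limits are followed literally. The scanner may in practice already cover the whole aorta, but the protocol does not show it.

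The harm is lost coverage. No bias between the blinded arms and no change in treatment difference, power or sample size is claimed. The dose total and risk are arithmetically right for the stated CT dose. Whether that dose applies to a scan covering the whole aorta cannot be shown from the protocol.

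**What to change.** Reconcile sections 8.8, 8.9 and 13.5.4 with 9.1 and 13.5.6:

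- State one CT and PET range, with the same anatomical upper and lower limits at baseline and week 16, that covers the aorta named in the endpoints.
- Say which range the 1.0 mSv describes. Confirm or restate the CT dose, the 9.6 mSv total and the 0.048% risk for the reconciled range.
- Check that the participant information (Appendix V, not seen here) gives the same figures.

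The cost is protocol wording, matching scanner set-up instructions and one dose check. No procedure is added and no endpoint changes. The downside is that the stated dose may turn out somewhat higher if the 1.0 mSv was calculated for the shorter range.

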13.5.5 Reconstruction protocol

Reconstruction of attenuation-corrected images will be done using an ordered subset expectation maximization algorithm with point-spread function (PSF) and time-of-flight (three iterations, 24 subsets, matrix size 192 x 192, 4-mm Gaussian postprocessing filter).

13.5.6 Quantification of radiotracer uptake in target tissue

PET and CT data will be fused and analysed with PMOD v3.703 (PMOD Technologies, Zurich, Switzerland). CT and PET images will be reviewed for quality and the images are manually co-

Trial ID (EudraCT No.): 2017-003697-14	Date: 23.02.2018	Page Version 2.3
---	------------------	---------------------

registered to ensure optimal anatomical correlation. Image analysis will be performed in accordance with recent nuclear medicine imaging guidelines by one expert observer. For the aorta, measurements are made every 3 mm, starting above the aortic valve level and continuing to the aortic bifurcation, approximately 200 slices per patient. Measurements are made in the axial planes by drawing a region of interest (ROI) containing the arterial wall and the lumen in each slice. The maximum standardized uptake values (SUVmax) of FDG within each ROI are recorded as a time- and dose-corrected tissue radioactivity divided by body weight.

Blood SUVmean are measured by drawing small ROIs in the superior vena cava and then averaged to approach one single most accurate value for the circulating blood-pool signal in each individual. The target-to-background ratio (TBR) will be calculated from the ratio of the SUV of the artery compared with background venous activity. Aortic FDG uptake will be assessed using the average TBRmax. Subcutaneous adipose tissue inflammation will be assessed and compared as SUVmax and TBR based on SUVmax. Targets are truncal subcutaneous adipose tissue localized beneath psoriatic plaques as indicated by the investigator.

Splenic inflammation is measured using mean standardised uptake values (SUV_{mean}) and the spleen-to-liver ratio (SLR) in accordance with current recommendations and previously published methodology ⁶³⁻⁶⁶. Spleen volume of interest (VOIs) are drawn on five adjacent axial slices covering the central part of the organ, whereas liver VOIs are drawn on six adjacent axial slices in the right lobe.

14 Adverse events

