13.2 Assessments performed only at screening/baseline

Assessments performed only at the screening and/or baseline visit include: assessment of

Trial ID (EudraCT No.): 2017-003697-14	Date: 23.02.2018	Page Version 2.3
---	------------------	---------------------

elegibility criteria, demographics, medical history, height, and weight. These are described in further detail below. Laboratory tests include hepatitis B, hepatitis C, HIV-1, HIV-2, T-spot, and serum pregnancy test. Varicella zoster antibody analysis may be relevant in some subjects. Procedures include chest X-ray.

A pre-treatment chart is completed before initiation of treatment according to national guidelines (Appendix III)

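### The only written SUV formula puts body weight on the wrong side, and no weighing is scheduled at the baseline scan; this touches only the adipose SUVmax endpoint

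*Protocol*

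**What the plan says.** Section 13.5.6 describes slice-by-slice aortic measurement and says that the SUVmax in each region of interest is "recorded as a time- and dose-corrected tissue radioactivity divided by body weight". No other SUV formula appears in the protocol. The next paragraph of that section covers fat: "Subcutaneous adipose tissue inflammation will be assessed and compared as SUVmax and TBR based on SUVmax". It gives no formula of its own.

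Three kinds of endpoint are built from SUV:

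- Aortic endpoints, whole vessel (primary) and subsegments: "The target-to-background ratio (TBR) will be calculated from the ratio of the SUV of the artery compared with background venous activity".
- Spleen: "Change in the spleen-to-liver ratio (SLR) based on splenic and liver mean standardised uptake values".
- Adipose tissue, listed under additional secondary objectives in section 9.1: "Change in the average of maximum SUV values (MeanSUV_{max}) of the abdominal" subcutaneous fat, together with its association with change in PASI.

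On weight, the Section 7 schedule marks a measurement at screening (week -4) and at visit 4 (week 16). It marks FDG-PET/CT at visit 2 (week 0) and visit 4. Section 13.2 opens with "Assessments performed only at the screening and/or baseline visit include: assessment of", and the list that follows ends with "height, and weight. These are described in further detail below". Section 13.4.1 says that weight follows the schedule, and section 13.1 sends the reader to the schedule for what is done at each visit.

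**The concern.** SUV exists to make uptake comparable between people who receive the same tracer activity but differ in size. The protocol plans about the same activity for everyone ("FDG will be administered intravenously (approximately 200 MBq") with no stated scaling to weight, and it admits subjects up to 150 kg. The weight term therefore carries real information. If it sits on the wrong side, heavier subjects count for less, and a change in weight moves the value in the wrong direction.

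A second question is which weight enters the calculation. The change in adipose MeanSUVmax compares two scans. The week-16 scan has a weighing at the same visit and the baseline scan does not, while section 13.2 reads as though weight were not repeated after baseline. What is at stake is one additional secondary endpoint and its association with PASI.

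**Working it through.** The protocol states no numerical result on this point, so there is no figure to reproduce. The check is algebra plus a comparison of visits.

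**Notation.** C is decay-corrected tissue activity concentration, D injected activity, W body weight.

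**1. The formula.**

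- Standard: SUV = C / (D / W) = C × W / D.
- As written: (C / D) / W = C / (D × W) = SUV / W².

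**2. Where it cancels.** TBR and SLR each divide two SUVs from the same scan, so D and W drop out. With tissue activities 5.0 and 2.0, the ratio is 2.5 under either formula. Adipose MeanSUVmax has no denominator from the same scan, so W stays.

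**3. Size under the literal reading only.** The weights and weight changes here are illustrative and do not come from the protocol, apart from the 150 kg limit.

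- Two subjects with the same true SUV at 70 and 110 kg: (110/70)² = 2.47, so their recorded values differ about 2.5-fold.
- 150 kg against 75 kg: (75/150)² = 0.25, so the heavier subject's value, and its change, count a quarter as much.
- True SUV unchanged, weight up 3%: 1/1.03² - 1 = -5.7%. Weight down 3%: 1/0.97² - 1 = +6.3%.

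**4. Which weight is available (Section 7 schedule).**

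| | Screening (week -4) | Visit 2 (week 0) | Visit 3 (week 6) | Visit 4 (week 16) |
|---|---|---|---|---|
| Weight | yes | no | no | yes |
| FDG-PET/CT | no | yes | no | yes |

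Following the schedule, the baseline SUV uses a weight taken about four weeks earlier and the week-16 SUV uses a current one.

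**5. Size with the standard formula.** Let the weight on the day of the baseline scan be (1 + g) times the screening weight. The SUV computed from the screening weight, divided by the correct one, is 1/(1 + g).

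- g = +1%: 1/1.01 - 1 = -1.0%.
- g = +5%: 1/1.05 - 1 = -4.8%. g = -5%: 1/0.95 - 1 = +5.3%.
- A weight wrong by 1 kg in 90 kg: 1/90 = 1.1%.

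The protocol gives no figure for weight drift between screening and baseline. The 1-5% range is an assumption.

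**6. Direction.** Section 12.2 places the first dose at visit 2, after the baseline scan. Drift between screening and that scan therefore precedes treatment and has no reason to differ by arm. It adds variability to the change score, and any shift common to both arms drops out of the treatment difference.

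**The case against.** Four points can be made in the protocol's favour.

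- The sentence belongs to the aortic paragraph, and the values it describes feed only TBR. The adipose endpoint is named by the standard term SUV. This stands in part: the sentence is not a definition written for fat, but it is the only one offered, and the adipose measure follows it in the same section.
- Section 13.5.6 names dedicated software (PMOD) and analysis to imaging guidelines by an expert observer. A loose rendering of correction for dose per body weight is more plausible than a planned inversion. This stands. A reader might infer that the adipose results will be wrong 2.5-fold or by 6%; the protocol does not support that, because nothing in it says that SUV will be worked out by hand from this sentence.
- A reader might also infer from section 13.2 that the week-16 SUV could rest on a weight 20 weeks old. Sections 13.1 and 13.4.1 both defer to the schedule, which has a weighing at visit 4. What is left is a conflict of wording in 13.2.
- Section 13.2 allows screening and/or baseline, so a weighing at visit 2 is permitted. True, but the schedule does not provide for one, and correct software still needs a weight to be entered.

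Adipose tissue is also to be assessed as TBR, where weight cancels. That limits the damage, but the endpoint listed in section 9.1 is MeanSUVmax.

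**Conclusion.** The point holds in a limited form and is minor. The protocol's one SUV formula is wrong as written, and it should match what the software computes. Separately, and whichever formula is applied, the absolute adipose endpoint has no same-day weight at baseline. Assuming 1-5% drift over about four weeks, the baseline adipose SUV is off by about 1-5%, which is expected to add noise and not to favour either arm.

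The larger distortions depend on the literal formula actually being used, which is unlikely. The primary endpoint, the aortic subsegments and SLR are ratios and are unaffected. The sample size rests on aortic TBR and does not change.

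**What to change.** - In section 13.5.6, define SUV as decay-corrected tissue activity concentration divided by (injected dose / body weight), and say that the weight is the one measured on the day of each scan.
- In the Section 7 schedule, add weight at visit 2 and keep it at visit 4.
- In section 13.2, take weight out of the list of assessments done only at screening or baseline, or reword the list so that it agrees with the schedule.

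The cost is a few lines of text and one weighing at a visit that already takes place.
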